## 5.4 BLINDING

### 5.4.1 Blinding Procedures

This study will employ a double-blind study design. The study drug and matching placebo tablets will be identical in appearance.

As this is an early phase study, the Sponsor may perform unblinded interim reviews of the data during the course of the study. An interim snapshot of the study database may be taken after completion of the clinical conduct of each cohort from the corresponding treatment arm.

### 5.4.2 Breaking the Blind

CCI [REDACTED] will be responsible for maintaining the blind throughout the study. If a subject becomes seriously ill or pregnant during the study, the blind will be broken (via IRT) only if knowledge of the administered study drug will affect that subject's available treatment options. In the event of a medical emergency requiring identification of the study drug administered to an individual subject, the investigator will make every attempt to contact CCI [REDACTED] to explain the need for unblinding. The investigator will be responsible for documenting the time, date, reason for the code break, and the names of the personnel involved.

## 5.5 TREATMENT COMPLIANCE

Treatment adherence will be assessed by a study medication log (patient diary), which will be completed by the clinic staff for in clinic doses and by the participant or mobile nursing staff for out of clinic doses.

The date and time of study drug administration will be recorded on the appropriate page of the eCRF. If a subject is not administered study drug, the reason for the missed dose will be recorded.

CCI

CCI

## 5.6 PRIOR AND CONCOMITANT MEDICATIONS

Information regarding prior medications taken by the subject within the 30 days before signing the informed consent form (ICF) as well as concomitant medications taken after starting study drug will be recorded in the subject's eCRF. Any concomitant medication deemed necessary for the welfare of the subject during the study may be given at the discretion of the investigator. This includes standard-of-care treatments/therapies for dengue should subjects deteriorate on-study due to their dengue infection. If a prohibited

concomitant medication is taken, a joint decision will be made by the investigator and the sponsor to continue or discontinue the subject from the study based on the time the medication was administered, its pharmacology and PK, and whether the use of the medication will compromise the safety of the subject or the interpretation of the data. The investigator is responsible for ensuring that details regarding the medication are adequately recorded in the eCRF. Prior and concomitant medications and therapies will be coded using the latest version of the World Health Organization Drug Dictionary.

### 5.6.1 Prohibited Therapy

Use of the following therapies is prohibited from Screening/Day 1 (unless otherwise specified below) until study completion or early termination, as described below:

- Any previously received investigational or approved vaccine for dengue
- Any antiviral drug within 30 days or within 5 half-lives (whichever is longer) of the active drug or metabolite (for long-acting antivirals)
- Exposure to another investigational agent within 30 days or 5 half-lives, whichever is longer, prior to study drug administration
- Concomitant use of herbal or natural supplements or grapefruit juice (e.g. St. John's Wort, echinacea, milk thistle). A washout period of at least 7 days must be observed prior to study drug dosing, if the investigator feels that they can be safely discontinued or substituted for the duration of the study
- Use of anticoagulant or antiplatelet drugs
- Use of medications for treatment of inflammatory bowel disease
- Use of immunosuppressive drugs including systemic corticosteroids (defined as prednisone equivalent of > 10 mg/day for > 2 weeks; inhaled or topical corticosteroids are allowed)
- Use of P-glycoprotein (P-gp) inducers and inhibitors as described below.
  - Note: hydroxychloroquine and amiodarone are prohibited within 3 months prior to screening and during the study.

CCI

P-gp inhibitors should be safely discontinued or substituted approximately 12 hours prior to the first dose of AT-752. Patients may resume use of the discontinued or substituted P-gp inhibitor approximately 12 hours after the final dose of AT-527. If the P-gp inhibitors cannot be safely discontinued or substituted, the subject must not be enrolled.

Note: Hydroxychloroquine and amiodarone are prohibited within 3 months prior to screening and during the study.

For a list of P-gp inhibitors, refer to <https://go.drugbank.com/categories/DBCAT002667>

The following P-gp inducers are prohibited:

- Anticonvulsants: carbamazepine, phenytoin, phenobarbital, oxcarbazepine
- Rifamycins: rifabutin, rifampin, rifapentine
- St. John's Wort

CCI

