**STUDY DESIGN:**

This study evaluates the safety, PK, and PD of AT-752 and will enroll approximately 60 subjects that meet the inclusion/exclusion criteria. Following screening and informed consent, eligible subjects will be randomized to receive either AT-752 or matching placebo orally 3 times a day (TID) for 5 days in Cohort 1 of the study. Subsequent cohorts will receive AT-752/placebo either twice a day (BID) or TID, as described below. Randomization will be stratified by geographic region. Standard-of-care treatment, including acetaminophen, will be permitted during the study.

At screening, information including demographics, medical history (including time since illness onset), and concomitant medications will be gathered from potential subjects. Any clinical care necessary throughout the study, such as supportive care, will be at the discretion of the investigator and institutional guidelines. Subject eligibility will be confirmed at the screening visit. Randomization and the initial dosing should occur on the same day as screening, if possible. Initial dosing should occur no later than 24 hours after screening.

For TID dosing, subjects will receive doses in the morning, at mid-day, and in the evening. TID doses will be separated by approximately 8 hours. [For BID dosing, subjects will receive doses in the morning and in the evening. BID doses will be separated by approximately 12 hours.] Subjects can continue participation even if hospitalized or using mobile nursing during the study, depending on site availability and subject decision. Subjects will be discharged on Day 6 (after end of treatment) if hospitalized, and asked to return on Day 7, Day 8, and Day 14 ( $\pm 1$  day) with a final safety follow-up performed on Day 28 ( $\pm 3$  days). For clinical sites that decide to use mobile nursing, some of the subsequent visits (Days 2-5,

Days 7-8, and Day 14) may be performed at investigator discretion through mobile nursing. The Day 1, Day 6, and Day 28 visits must be conducted at the clinical site.

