**Exclusion Criteria:**

A patient who meets any of the following criteria will be excluded from participation in this study:

1. Pregnant at screening or plans to become pregnant within 90 days of screening
2. Female patient who is breastfeeding or plans to breastfeed during the study period
3. Has previously received any investigational or approved vaccine for dengue
4. Previous history of HIV, active chronic hepatitis B infection, or current hepatitis C infection (from medical history)
5. Use of any antiviral drug within 30 days or within 5 half-lives (whichever is longer) of the active drug or metabolite (for long-acting antivirals) of screening
6. Currently enrolled in or plans to participate in another clinical trial with an investigational agent or device that will be received during the study reporting period.
7. Exposure to another investigational agent within 30 days or 5 half-lives, whichever is longer, prior to study drug administration
8. Concomitant use of herbal or natural supplements (e.g. St. John's Wort, echinacea, milk thistle) or grapefruit juice. These should be discontinued at screening if the investigator feels that they can be safely discontinued or substituted for the duration of the study.
9. Patients with chronic medical conditions that put them at risk for severe dengue, including uncontrolled diabetes mellitus, severe asthma requiring oral steroids, or admission to the hospital in the previous 6 months for cardiac disease.
10. Current use of anticoagulant or antiplatelet drugs or documented medical history of bleeding disorders
11. Malabsorption syndrome or other conditions that would interfere with enteral absorption
12. Immunocompromised due to use of immunosuppressive drugs including systemic corticosteroids (inhaled or topical corticosteroids are allowed) or immunocompromised due to any current disease or condition
13. Use of P-glycoprotein (P-gp) inducers and inhibitors as described in [Section 5.6.1](#). *Note: hydroxychloroquine and amiodarone are prohibited within 3 months prior to screening and during the study.*
14. Evidence of severe dengue disease including:
  - Severe plasma leakage leading to shock or fluid accumulation with respiratory distress
  - Severe bleeding (including any subjects with hemoglobin levels <13.0g/dL in males and <11.0g/dL in females).

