After eligibility is determined at screening, the initial dose of study drug can be administered after randomization and within 24 hours of screening. This can occur before obtaining the results of the DENV serotype testing and viral load assessments. If possible, administer the initial dose of study drug on the same day as screening.

Evaluations that must be completed before administering the initial dose include:

- Determining eligibility criteria
- Obtaining informed consent
- Recording demographics, medical history, and concomitant medications
- Complete physical examination. If the initial dose of study drug is administered on the same day as screening, the results of the complete physical examination at screening will be substituted for symptom-directed physical examination on Day 1
- Vital signs. On Day 1, vital sign measurements should be performed before any scheduled blood collections and prior to administration of study drug. If the initial dose of study drug is administered on the same day as screening, the results of the vital signs obtained at screening will be used for the Day 1 vital sign results. Note that oral temperature is also to be collected during the dosing period at least 4 times a day (morning, mid-day, late afternoon, evening; approximately every 4 hours while subjects are awake)
- Triplicate consecutive 12-lead ECG.

- Chemistry, hematology, coagulation, and urinalysis (with microscopy). At screening, samples should be collected for urinalysis (with microscopy), but subjects can begin treatment with study drug before the results are obtained unless medically required to establish eligibility (at investigator's discretion). If the initial dose of study drug is administered on the same day as screening, the screening results for these tests will be used for the Day 1 results. Results from standard-of-care evaluations that are available prior to informed consent are accepted if performed within 24 hours of screening
- SARS-CoV-2 rapid test, rapid influenza diagnostic test, and urine pregnancy testing
- DENV serotype testing. Subjects can begin treatment with study drug before the DENV-serotype results are obtained, but the samples should be obtained before dosing

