##### 4.1 INCLUSION CRITERIA

A patient must meet the following criteria to be eligible for participation in this study:

1. 18-55 years of age at time of screening
2. Fever  $\geq 38^{\circ}\text{C}$  (or feeling feverish) with onset during the previous 60 hours
3. Positive test confirming DENV on a NS1 antigen test or RT-PCR assay
4. Negative rapid diagnostic test results for SARS-CoV-2 and Influenza A and B
5. Body mass index (BMI) of 18 to 30  $\text{kg/m}^2$

6. Provides written informed consent prior to initiation of any study procedures
7. Able to understand and agrees to comply with planned study procedures and be available for all study visits
8. Males and females of childbearing potential must agree to use protocol-specified methods of contraception as described in [Section 4.1.1](#)
9. Male subjects must agree to not donate sperm from the first dose through 90 days after the last dose of study drug

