#### **4.2 EXCLUSION CRITERIA**

A patient who meets any of the following criteria will be excluded from participation in this study:

1. Pregnant at screening or plans to become pregnant within 90 days of screening
2. Female patient who is breastfeeding or plans to breastfeed during the study period
3. Has previously received any investigational or approved vaccine for dengue
4. Previous history of HIV, active chronic hepatitis B infection, or current hepatitis C infection (from medical history)
5. Use of any antiviral drug within 30 days or within 5 half-lives (whichever is longer) of the active drug or metabolite (for long-acting antivirals) of screening
6. Currently enrolled in or plans to participate in another clinical trial with an investigational agent or device that will be received during the study-reporting period
7. Exposure to another investigational agent within 30 days or 5 half-lives, whichever is longer, prior to study drug administration
8. Concomitant use of herbal or natural supplements or grapefruit juice (e.g. St. John's Wort, echinacea, milk thistle) or grapefruit juice. These should be discontinued at screening if the investigator feels that they can be safely discontinued or substituted for the duration of the study.
9. Patients with chronic medical conditions that put them at risk for severe dengue, including uncontrolled diabetes mellitus, severe asthma requiring oral steroids, and admission to the hospital in the previous 6 months for cardiac disease
10. Current use of anticoagulant or antiplatelet drugs or documented medical history of bleeding disorders
11. Malabsorption syndrome or other conditions that would interfere with enteral absorption
12. Immunocompromised due to use of immunosuppressive drugs including systemic corticosteroids (inhaled or topical corticosteroids are allowed) or any current disease or immunocompromised due to any current disease or condition
13. Use of P-glycoprotein (P-gp) inducers and inhibitors as described in [Section 5.6.1](#). *Note: hydroxychloroquine and amiodarone are prohibited within 3 months prior to screening and during the study.*

14. Evidence of severe dengue disease including:

- Severe plasma leakage leading to shock or fluid accumulation with respiratory distress
- Severe bleeding (including any subjects with hemoglobin levels <13.0g/dL in males and <11.0g/dL in females)

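### The protocol asks for at least 7 days' washout of herbal supplements and grapefruit juice in Section 5.6.1, but exclusion 8 has them stopped at screening, with first dosing due within 24 hours

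*Protocol*

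**What the plan says.** Three parts of the protocol bear on this.

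- **Section 5.6.1 (Prohibited Therapy).** The section opens by stating when its prohibitions apply: "Use of the following therapies is prohibited from Screening/Day 1 (unless otherwise specified below) until study completion or early termination". One listed item is "Concomitant use of herbal or natural supplements or grapefruit juice (e.g. St. John's Wort, echinacea, milk thistle". For that item it adds: "A washout period of at least 7 days must be observed prior to study drug dosing". This is conditional on the investigator judging it safe to stop or replace the product.
- **Exclusion 8 (synopsis and Section 4.2).** It names the same products, with the same condition about the investigator's judgement. The instruction is different: "These should be discontinued at screening if the investigator feels that they can be safely discontinued or substituted for the duration of the study". No washout is stated in either copy.
- **Dosing window.** The synopsis says "Initial dosing should occur no later than 24 hours after screening". Section 3 and the notes to Table 3-1 say the same, and Section 3.1.1 says that "the initial dose of study drug can be administered after randomization and within 24 hours of screening". All prefer dosing on the day of screening. SAP Section 3.1 repeats the 24-hour limit.

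St. John's Wort appears a further time. Section 5.6.1 also lists it as a prohibited P-gp inducer, and exclusion 13 applies that list through a cross-reference to Section 5.6.1.

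**The concern.** A site that screens a current user finds one passage telling it to stop the product at screening and another telling it not to dose until at least 7 days have passed. In an acute infection with a one-day screening-to-dose window, both cannot be followed for that patient. No passage exempts these products from the washout or lengthens the window for patients who need it.

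Two features of the trial make it worth settling in advance. About 60 subjects at about 40 sites is an average of 60 / 40 = 1.5 per site, so sites could well read the text differently without anyone noticing a pattern. And Protocol Section 10.2.4.2 does not allow prospective waivers of eligibility criteria, so a site cannot resolve the question by asking permission case by case.

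What is at stake is consistent eligibility and consistent recording of deviations. If the Section 5.6.1 rule counts, a patient dosed after stopping at screening is a deviation. If exclusion 8 alone counts, the same patient is not. Any effect on the analyses follows from that classification.

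**Working it through.** No sample size, power or error rate is involved, and the plan gives no figure to reproduce. The check is interval arithmetic on stated times.

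**Inputs**

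| Quantity | Value | Source |
|---|---|---|
| Required washout before first dose | at least 7 days = 7 × 24 = 168 h | Protocol 5.6.1 |
| Time of stopping | at screening | Exclusion 8, synopsis and 4.2 |
| Screening to first dose | 0 to 24 h | Synopsis (Study Design), Sections 3 and 3.1.1, notes to Table 3-1 |
| Fever onset before screening | up to 60 h ("with onset during the previous 60 hours") | Protocol 4.1 |
| Start of treatment to end of follow-up | 28 to 31 days | Synopsis, Estimated Study Duration |
| Maximum participation | 32 days | Synopsis, Estimated Study Duration |

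**Step 1. Stop at screening, dose on schedule.** Washout achieved equals the screening-to-dose interval, 0 to 24 h. Shortfall = 168 − 24 = 144 h to 168 − 0 = 168 h, that is 6 to 7 days. Section 5.6.1 is not met.

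**Step 2. Stop at screening, wait for the washout.** The first dose falls at 168 h. Overrun of the dosing window = 168 − 24 = 144 h.

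Participation, using the protocol's own 28 to 31 days, becomes 7 + 28 = 35 to 7 + 31 = 38 days, against 32. A final visit at the early edge of its ±3-day window (Day 25) would give about 7 + 25 = 32 days, so the maximum could be exceeded but need not be.

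The longest time from fever onset to first dose becomes 60 + 168 = 228 h (9.5 days), against 60 + 24 = 84 h (3.5 days) under the 24-hour window.

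**Step 3. What would satisfy both.** The last use must be at least 168 − 24 = 144 h before screening if dosing is at 24 h, or 168 h before screening if dosing is at once. Fever began at most 60 h before screening, so such a patient stopped the product before becoming ill. That patient was not a user at screening, and the instruction in exclusion 8 does not concern them.

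**Step 4. St. John's Wort.** Set side by side, exclusion 8 has it stopped at screening, the herbal item of Section 5.6.1 asks for 7 days, and the inducer list in Section 5.6.1, applied by exclusion 13, prohibits it. The visible text gives no timing for inducers. Text next to that list is redacted, so a timing rule may exist there. The main conflict in Steps 1 and 2 does not rest on this item.

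**The case against.** The best defence is that the passages can be read together. Exclusion 8 does not say that stopping at screening waives Section 5.6.1, and the washout is a "must" while exclusion 8 and most statements of the 24-hour limit are a "should". On that reading the stricter text governs, a site does not enrol the user, and nobody breaks a rule.

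That stands as far as it goes. A deviation is not inevitable. A reader might infer that every user of these products necessarily breaks one rule. The documents do not support that: a patient whose last use was at least 7 days before dosing meets both, and a site that declines to enrol breaks neither. Nor does exclusion 8 itself authorise dosing within 24 hours. That limit comes from the design sections.

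But the combined reading leaves the exclusion 8 instruction with nothing to do, because no patient who stops at screening can complete 7 days inside the window. Treating the 24-hour limit as flexible only shifts the problem to late first dosing and possibly to the 32-day maximum.

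Two existing provisions reduce the consequences. Protocol Section 5.6 records medications from the 30 days before consent and provides a joint investigator–sponsor decision when a prohibited concomitant medication is taken. SAP Sections 5.2 and 5.3 already plan listings of all deviations and of eligibility deviations. Neither tells a site whom it may dose, and a listing captures a case only if it is recognised as a deviation, which is the point in doubt.

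A reader might also infer that pharmacokinetic results would be distorted. Among the products named in exclusion 8, the documents identify only St. John's Wort as acting on P-gp. For echinacea, milk thistle and grapefruit juice they give no such statement, so a general claim is not supported.

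**Conclusion.** The inconsistency is real and minor. For a patient using one of these products at screening who stops then and is dosed on schedule, the washout is short by 144 to 168 hours out of 168. For the same patient held for 7 days, dosing is 144 hours outside the window. The conclusion assumes only that the two passages cover the same products, which they name, and that the dosing window applies to every patient, since no exception is given.

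The effect on the analyses is possible but not established. The number of users is not stated. One patient would be 1/15 = 6.7% of a full active arm, but this says nothing about how many are affected.

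It might be inferred that such patients drop out of the per-protocol set. That requires a major violation, which SAP Section 4.3 ties to an impact on patient safety or data quality, and no passage classes a short supplement washout in this way. The modified intent-to-treat set, used for the primary analysis, depends on randomisation, dosing and virology measurements. The PK set depends on dosing and sufficient concentration data. Neither is defined by this rule.

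**What to change.** Reconcile Section 5.6.1 with exclusion 8 in both the synopsis and Section 4.2, and with the dosing window in the synopsis, Sections 3 and 3.1.1 and the notes to Table 3-1, so that one consistent rule says whether and when a recent user may be dosed. State in the same place how St. John's Wort is handled, given that it falls under both the herbal item and the inducer list. Which rule is right is a clinical decision for the sponsor, and this review does not propose one.

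For patients already enrolled, apply the reconciled rule when compiling the deviation listings already planned in SAP Sections 5.2 and 5.3. Before unblinding, state whether a short washout counts as a major violation for the per-protocol set.

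The cost is protocol wording, handled through the amendment process in Section 10.2.4.1, with one clarifying sentence in the SAP. No new data collection is needed, because prior medications over the 30 days before consent are already recorded.
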